mL	milliliter(s)
MMF	Mycophenolate mofetil
NSAIDs	Nonsteroidal Anti-Inflammatory Drugs
Commercially Confidential Information	
PDAI	Pemphigus Disease Area Index

Commercially Confidential Information

PK pharmacokinetic(s)
Commercially Confidential Information

PV Pemphigus vulgaris

RA Rheumatoid Arthritis

RAP Reporting and Analysis Plan

RBC red blood cell(s)

REB Research Ethics Board

RF rheumatoid factor

SAE serious adverse event

s.c. subcutaneous

SAD single ascending dose

SD standard deviation

SGOT serum glutamic oxaloacetic transaminase

SGPT serum glutamic pyruvic transaminase

SoC standard of care

TBL total bilirubin

TK toxicokinetic(s)

TMDD Target-mediated drug disposition

ULN upper limit of normal

Commercially Confidential Information

WBC white blood cell(s)

WOCBP women of child-bearing potential

Pharmacokinetic definitions and symbols

AUC _{inf}	The area under the plasma (or serum or blood) concentration-time curve from time zero to infinity [mass x time / volume]
AUC _{last}	The area under the plasma (or serum or blood) concentration-time curve from time zero to the time of the last quantifiable concentration [mass x time / volume]
C _{max}	The observed maximum plasma (or serum or blood) concentration following drug administration [mass / volume]
T _{1/2}	The terminal elimination half-life [time]
T _{max}	The time to reach the maximum concentration after drug administration [time]

Glossary of terms

Assessment	A procedure used to generate data required by the study.
Enrollment	Point/time of subject entry into the study; the point at which informed consent must be obtained (i.e. prior to starting any of the procedures described in the protocol).
Investigational drug	The study drug whose properties are being tested in the study; this definition is consistent with US CFR 21 Section 312.3 and is synonymous with “investigational new drug” or “investigational medicinal product”.
Investigational treatment	
All investigational drug(s) whose properties are being tested in the study as well as their associated treatment controls.
 
This includes any placebos, any active controls, as well as approved drugs used outside of their indication/approved dosage or tested in a fixed combination.
 
Investigational treatment generally does not include other treatments administered as concomitant background therapy required or allowed by the protocol when used within approved indication/dosage.

Subject number	A number assigned to each subject who enrolls in the study. When combined with the center number, a unique identifier is created for each subject in the study.
Period	A minor subdivision of the study timeline; divides phases into smaller functional segments such as screening, baseline, titration, washout, etc.
Premature subject withdrawal	Point/time when the subject exits from the study prior to the planned completion of all study drug administration and assessments; at this time all study drug administration is discontinued and no further assessments are planned.
Randomization number	A unique identifier assigned to each randomized subject, corresponding to a specific treatment arm assignment.
Study completion	Point/time at which the subject came in for a final evaluation visit or when study drug was discontinued whichever is later.
Study drug/treatment	Any drug (or combination of drugs) administered to the subject as part of the required study procedures; includes investigational drug, active drug run-ins or background therapy.
Study drug discontinuation	Point/time when subject permanently stops taking study drug for any reason; may or may not also be the point/time of premature subject withdrawal.

Subject	An individual who has consented to participate in this study. The term Subject may be used to describe either a healthy volunteer or a patient.
Variable	Information used in the data analysis; derived directly or indirectly from data collected using specified assessments at specified timepoints.

Commercially Confidential Information

Commercially Confidential Information

Commercially Confidential Information

Commercially Confidential Information

Commercially Confidential Information

Commercially Confidential Information

Commercially Confidential Information

Commercially Confidential Information

Commercially Confidential Information

Commercially Confidential Information

Protocol synopsis

Protocol number	CVAY736X2203
Title	A randomized, partial-blind, placebo-controlled trial evaluating the efficacy, safety, pharmacokinetics and pharmacodynamics of VAY736 in the treatment of patients with pemphigus vulgaris
Brief title	Study of efficacy and safety of VAY736 in patients with Pemphigus vulgaris
Sponsor and Clinical Phase	Novartis Phase II
Investigation type	Drug
Study type	Interventional
Purpose and rationale	To determine if a single intravenous dose of VAY736 can reduce disease activity in Pemphigus vulgaris. As determined by the change in Pemphigus Disease Area Index (PDAI) compared to placebo. The study will also provide safety and tolerability information for VAY736 in PV patients.
Primary Objective(s) and Key Secondary Objective	To compare the efficacy of a single i.v dose of VAY736 relative to placebo in reducing clinical disease activity of pemphigus vulgaris patients, as determined by the change in Pemphigus Disease Area Index (PDAI) between baseline and 12 weeks
Secondary Objectives	
 To evaluate the safety and tolerability of VAY736 in patients with PV To evaluate the effect of VAY736 in PV patients as assessed by the Autoimmune Bullous Skin disease Intensity Score (ABSIS) at 12 weeks To evaluate the effect of VAY736 in PV patients as assessed by Investigator Global Assessment (IGA) at 12 weeks To evaluate VAY736 pharmacokinetics in serum in PV patients
Study design	
This is a non-confirmatory, randomized, partial-blind, placebo-controlled trial evaluating the efficacy, safety, pharmacokinetics ^{Commercially} Confidential Information of VAY736 in the treatment of patients with pemphigus vulgaris.
 
Approximately 24 patients with mild-moderate active PV will be randomly assigned in a blinded fashion to one of three single dose treatment arms. Recruitment will be staggered and progression between doses is dependent upon a safety review milestone.
 
In the pre-safety review period, 9 patients will be randomized to a single dose of either 3 mg/kg VAY736 (6 patients) or placebo (3 patients). Once patients have achieved Week 6, a safety review will take place. If there are no safety signals, recruitment will restart into the 3 mg/kg (3 patients) and placebo (3 patients) arms and commence to the 10 mg/kg arm (9 patients). Following the single dose on Day 1, standard of care medications will be maintained at a stable level until 'disease control' in signs/symptoms of PV. The standard of care medication will then be tapered to safely deliver the patient to the lowest dose level required to maintain control of the disease.
 
Patients will enter into a double-blind follow up period for 24 weeks post dose, at which point their treatment will be unblinded. Patients that received VAY736 will then enter into a long-term follow up ^{Commercially Confidential Information}. Patients that received placebo will be offered open-label single dose IV VAY736 treatment.

Population
	
The study population will be comprised of male and female Pemphigus vulgaris patients, aged between 20 and 70 years, inclusive.
 
It is planned that up to approximately 32 patients may be enrolled (randomized) into the study; at least 24 patients are expected to complete the study.


Inclusion criteria
	
All patients
 
 • Diagnosis of PV according to (i) presence of blisters or erosions of the skin or mucous membranes, plus (ii) characteristic documented histological findings in the skin, plus (iii) characteristic findings from direct immunofluorescence in Commercially Confidential Information . If results are not available, biopsies and a blood sample have to be taken at screening to confirm diagnosis. • Presence of mild to moderate active PV at Baseline as defined by a PDAI score between 20 and 60 (inclusive) or for a PDAI below 20: an IGA of 2 to 3 (e.g. at least 1% but not more than 10 % BSA involvement). • On a stable dose(s) of oral corticosteroid +/- adjuvant therapy of azathioprine or mycophenolate mofetil. Requirements for these standard-of-care (SoC) medications are: 
 • Oral corticosteroids alone, with steroid dose to be equivalent to prednisone ≥ 15 mg per day but no greater than 2 mg/kg/day; or • Oral corticosteroid + azathioprine, with steroid dose to be equivalent to prednisone ≥ 2.5 mg per day but no greater than 1 mg/kg/day, and azathioprine with no specific daily dose requirement; or • Oral corticosteroid + mycophenolate mofetil, with steroid dose to be equivalent to prednisone ≥ 2.5 mg per day but no greater than 1 mg/kg/day, and mycophenolate mofetil with no specific daily dose requirement. 
SoC medications considered stable if the daily dose has not changed within the 7 days preceding the day of dosing (Day 1) for oral corticosteroid, or within the 14 days preceding the day of dosing (Day 1) for azathioprine and mycophenolate mofetil.
 
Open-label patients (i.e. for placebo-treated patients)
 
 • Presence of mild to moderate active PV at unblinding, as defined by a PDAI score more than 10. • On a stable dose(s) of oral corticosteroid +/- adjuvant therapy of azathioprine or mycophenolate mofetil. Requirements for these standard-of-care (SoC) medications are: 
 • Oral corticosteroids alone, with steroid dose to be equivalent to prednisone ≥ 15 mg per day but no greater than 2 mg/kg/day; or • Oral corticosteroid + azathioprine, with steroid dose to be equivalent to prednisone ≥ 2.5 mg per day but no greater than 1 mg/kg/day, and azathioprine with no specific daily dose requirement; or • Oral corticosteroid + mycophenolate mofetil, with steroid dose to be equivalent to prednisone ≥ 2.5 mg per day but no

	
greater than 1 mg/kg/day, and mycophenolate mofetil with no specific daily dose requirement.
 
SoC medications considered stable if the daily dose has not changed within the 7 days preceding the day of dosing (Day 1) for oral corticosteroid, or within the 14 days preceding the day of dosing (Day 1) for azathioprine and mycophenolate mofetil.


Exclusion criteria
	
All patients
 
 • Known hypersensitivity to any constituents of the study drug, to murine, chimeric or human antibodies, or to drugs of similar chemical classes (e.g., IgG1 biologics). Also, known hypersensitivity to study drug premedication (paracetamol or acetaminophen) and H1 receptor blocker). • Prior use in the 12 months prior to Screening of any B-cell depleting therapy e.g., rituximab or other anti-CD20 mAb, anti-CD22 mAb, anti-CD52 mAb. • Use of prednisone or other systemic steroids for conditions other than pemphigus vulgaris within the 1 month prior to Baseline. • Use of topical steroids (or other topical treatment for PV) within 2 weeks prior to Baseline. • Recent previous treatment with phototherapy, biological therapy, immunosuppressive agents such as azathioprine (unless it is used as SoC medications for pemphigus treatment as per inclusion criteria # 5), dapsone, or methotrexate. The following washout period will be required for such patients to be eligible to participate in the trial: • 6 months washout prior to Screening for IVIg, plasmapheresis, immunoabsorption or i.v. or oral cyclophosphamide; • 3 months washout prior to Screening for etanercept, adalimumab, ustekinumab, infliximab or any other immunologically active biologic therapy; • 1 month washout prior to Screening for UVB/PUVA therapy, dapsone, methotrexate, and any systemic immunosuppressants or other systemic treatment for PV. • Active viral, bacterial or other infections at the time of Screening or Baseline, or history of recurrent clinically significant infection or of recurrent bacterial infections with encapsulated organisms. • Evidence of active or latent tuberculosis (TB), or inadequately treated infection with TB 
Decisions about management of previous treatments are left to the treating physician in line with the patients' choices, and should be conducted according to local standard of care best practice. The present protocol does not support stopping a medication if the sole purpose is to allow a patient to then become eligible to enter the study.
 
Open-label patients (i.e. for placebo-treated patients)
 
 • CBC laboratory values as follows: • Hemoglobin <10.0 g/dL • White blood cell count <3,000/μL • Platelets <100,000/μL • Absolute neutrophil count \leq1,500/μL

Investigational and reference therapy
	
VAY736 3 mg/kg; 10 mg/kg


Efficacy assessments
	
 • Pemphigus Disease Area Index • Autoimmune Bullous Skin disease Intensity Score • Investigator Global Assessment

Safety assessments
	
 • Physical examination • Vital signs • 12-Lead ECG • Hematology, Blood chemistry, Urinalysis • Adverse Events/Serious Adverse Events • Concomitant Medications 
Commercially Confidential Information

Other assessments
	
 • Pharmacokinetics 
Commercially Confidential Information


Data analysis
	
The change from baseline in PDAI skin and mucous membranes activity score will be analyzed using a mixed effects model for repeated measures including terms for the patient effect (as a random effect), treatment effect (VAY736 3 mg/kg, VAY736 10 mg/kg or placebo), follow-up time points and the interaction between time and treatment (all as fixed effects) adjusting for the baseline PDAI skin and mucous membranes score as a covariate. This statistical analysis model will include change from baseline data on the PDAI from all post-baseline time points at which it was recorded (i.e. weeks 3, 6, 9, 12, 16, 20 and 24) but the primary comparison is made for week 12. The analysis model may be adjusted for increases in SoC, if appropriate.
 
A positive sign of therapeutic effects will be considered to be a difference of at least 10 points in the change from baseline between the 10 mg/kg dose of VAY736 and placebo with a moderate level of evidence (i.e. 50%). Additionally there should be a high level of evidence (i.e. 90%) for a difference between the 10 mg/kg dose of VAY736 and placebo. The estimates of the posteriors probabilities of these criteria being met will be provided for each VAY736 dose separately and for the combined 3 mg/kg and 10 mg/kg doses, assuming standard non-informative prior Normal distributions. In case there is no difference between treatments on the PDAI at week 12 but significantly higher increases of SoC in the placebo arm, this may also be considered a sign of efficacy.
 
Secondary efficacy variables (i.e. change from baseline to week 12 measurements of PDAI total score and ABSIS) will be analyzed following a similar approach. The number and percentage of patients experiencing control of disease activity will be presented for each visit. The posterior distributions of the difference in proportions between each dose of VAY736 and placebo, given the data, will be estimated assuming a "neutral", non-informative Beta (1/3, 1/3) prior for each treatment group.
 
The number and percentage of patients in each category of response for the IGA will be presented for each visit.
 
Commercially Confidential Information

	Commercially Confidential Information	
Key words	Pemphigus vulgaris, pemphigus,	

Study Phase	Screening	Double-blind Period										Long term Follow-up ¹⁹		End of study (EoS)	
		Visit 1	Visit 2 Baseline/Dosing	Visit 3	Visit 4	Visit 5	Visit 6	Visit 7	Visit 8	Visit 9	Visit 10	Visit 11	Visits 12, 13 and 14		V515, V516
Weeks post-dose	-	0	1	2	3	6	9	12	16	20	24	32, 40, 52	76, 100		
Study day(s) ¹	-28 to -1	1	8	15	22	43	64	85	113	141	169	225, 281, 365	532, 700		
Allowed time window ¹	-	± 2 h for 24 h	± 2d	± 2d	± 3d	± 4d	± 4d	± 4d	± 7d	± 7d	± 7d	± 2 weeks			
Laboratory Safety Tests															
Hematology incl. differential WBC count	X	X, 24 h	X	X	X	X	X	X	X	X	X	X	X	X	X
Clinical chemistry	X	X, 24 h	X	X	X	X	X	X	X	X	X	X	X	X	
Urinalysis	X	X, 24 h	X	X	X	X	X	X	X	X	X	X	X	X	
Ig subset and total													X	X	
Hepatitis and HIV screen	X														
Alcohol test and Drug screen	X														
TB assessment	X														
Pregnancy (hCG) test ⁵	X	X			X	X	X	X	X	X	X	X	X	X	
FSH ⁶	X														
Premedication ⁷		X													
Study Drug administration ⁷		X													

Commercially Confidential Information

Commercially Confidential Information

Commercially Confidential Information

Study Phase	Screening	Double-blind Period										Long term Follow-up ¹⁹		End of study (EoS)
		Visit 1	Visit 2 Baseline/Dosing	Visit 3	Visit 4	Visit 5	Visit 6	Visit 7	Visit 8	Visit 9	Visit 10	Visit 11	Visits 12, 13 and 14	
Weeks post-dose	-	0	1	2	3	6	9	12	16	20	24	32, 40, 52	76, 100	
Study day(s) ¹	-28 to -1	1	8	15	22	43	64	85	113	141	169	225, 281, 365	532, 700	
Allowed time window ¹	-	± 2 h for 24 h	± 2d	± 2d	± 3d	± 4d	± 4d	± 4d	± 7d	± 7d	± 7d	± 2 weeks		
Pharmacokinetic blood sampling		X, 2, 24 h ¹²	X	X	X	X	X	X	X	X	X			X ²¹
Standardized Body Photographs		X			X	X	X	X	X	X	X	X		X
Pemphigus Disease Area Index (PDAI) ¹³	X	X			X	X	X	X	X	X	X	X		X
Investigator Global Assessment (IGA) ¹³	X	X			X	X	X	X	X	X	X	X		X
Autoimmune Bullous Skin disease Intensity Score (ABSIS) ¹³		X						X			X	X		X
Assessment of Disease activity questionnaire ¹³	X	X	X	X	X	X	X	X	X	X	X	X		X

Commercially Confidential Information

Code Break ¹⁷												X		
Adverse events, Serious adverse events ¹⁸	Assess continuously from signature of informed consent													

Legend

1. Allowed visit windows are to be scheduled in relation to Day 1 (Baseline/Dosing); Day 1 is the date by which subsequent visits are to be scheduled.
2. Review of inclusion/exclusion criteria, medical history and current conditions, plus measurement of body weight is performed at Baseline, Day 1, prior to dosing.
3. Assessments to be conducted locally at Screening to confirm presence of pemphigus vulgaris (PV) only where not previously performed and documented as part of the patient's regular medical care.
4. Vital signs: Sitting blood pressure and heart rate measurement required at all visits, plus standing measurements only at Screening and Baseline. During study drug administration, blood pressure and heart rate should be obtained every 30 minutes.
5. For women, serum pregnancy testing (human chorionic gonadotropin, hCG) is required screening and end of study regardless of reported reproductive/menopausal status. Urine pregnancy test will be performed at Baseline (Day 1) and every post-dose visit from Week 3 onwards, and may be conducted in addition at the discretion of the investigator or may be required more frequently by local practices, if a menstrual cycle is missed, or if potential pregnancy is otherwise suspected.
6. For postmenopausal women, FSH conducted at Screening to assist in confirming menopausal status.
7. Administration: VAY736 infusion over 1-2 hours following premedication with paracetamol (or acetaminophen) and a H1 receptor blocker.
- 8.
9. Commercially Confidential Information
- 10.
- 11.
12. PK samples on Day 1 to be taken (1) pre-dose, (2) at the end of infusion when the indwelling line is empty and (3) 24 h post-dose (start of infusion: \pm 2 h).
13. Assessment completed by the investigator.
14. Assessment completed by the patient.
15. Commercially Confidential Information
16. At the selected sites (refer to footnote 15) this sample will be collected after Week 12 if the IGA score increases by at least 1 compared to the previous visit in patients that have previously reached disease control.
17. At Week 24 the blind will be broken and patients who were on placebo will be offered the opportunity to receive open label VAY736 administration at Week 25, and will follow the same visit pattern as if re-starting from Day 1. Refer to [Section 5.5.8](#) for unblinding prior to Week 24.

18. Serious adverse events are reportable from time of signing informed consent until 30 days after patient has stopped study participation. During the second part of the long-term safety follow-up (from Week 76), only AEs related to VAY736 and/or to infection, potential malignant events and neutropenia will be recorded.

19.

Commercially Confidential Information

20.

Note: A patient may reach “disease control” in their PV disease between protocol-defined study visits. In such a circumstance, ad-hoc unplanned clinic visits or consultation over the phone is possible to review/alter a patient’s steroid dose.

21. Pharmacokinetic blood sampling is optional at the end of study

1 Introduction

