4.1 Inclusion criteria

All patients

Patients eligible for inclusion in this study have to fulfill **all** of the following criteria:

1. Written informed consent must be obtained before any assessment is performed.
2. Male and female patients 20 to 70 years of age inclusive (at the time of the Screening visit), and having passed Screening examinations by past medical history, physical examination, vital signs, electrocardiogram, and laboratory tests.
3. Diagnosis of PV according to (i) presence of blisters or erosions of the skin or mucous membranes, plus (ii) characteristic documented histological findings in the skin, plus (iii) characteristic findings from direct immunofluorescence in skin

Commercially Confidential Information

If results are not available, biopsies and a blood sample have to be taken at screening to confirm diagnosis.

4. Presence of mild to moderate active PV at Baseline as defined by a PDAI score between 20 and 60 (inclusive) or for a PDAI below 20: an IGA of 2 to 3 (e.g., at least 1% but not more than 10 % BSA involvement).

5. On a stable dose(s) of oral corticosteroid +/- adjuvant therapy of azathioprine or mycophenolate mofetil. Requirements for these standard-of-care (SoC) medications are:
 - Oral corticosteroids alone, with steroid dose to be equivalent to prednisone ≥ 15 mg per day but no greater than 2 mg/kg/day; or
 - Oral corticosteroid + azathioprine, with steroid dose to be equivalent to prednisone ≥ 2.5 mg per day but no greater than 1 mg/kg/day, and azathioprine with no specific daily dose requirement; or
 - Oral corticosteroid + mycophenolate mofetil, with steroid dose to be equivalent to prednisone ≥ 2.5 mg per day but no greater than 1 mg/kg/day, and mycophenolate mofetil with no specific daily dose requirement.
6. SoC medications considered stable if the daily dose has not changed within the 7 days preceding the day of dosing (Day 1) for oral corticosteroid, or within the 14 days preceding the day of dosing (Day 1) for azathioprine and mycophenolate mofetil. Patients must weigh in the range of 40 kg to 150 kg inclusive.
7. Able to communicate well with the investigator, to understand and comply with the requirements of the study.

Open-label patients (i.e. for placebo-treated patients)

1. Presence of mild to moderate active PV at unblinding, as defined by a PDAI score more than 10.

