6.4.3 Investigator global assessment (IGA)

An IGA score on a 0-4 scale will be used to assess each patient's PV disease activity as per the scale in [Section 21-Appendix 9](#) (modified from [Mahajan et al 2005](#)). IGA scores will be captured in the eCRF.

For the IGA, active PV lesions are defined as urticarial lesions, blisters and erosions which are not epithelialized. Erythematous patches and erosions which have healed to the extent that they are epithelialized are not included in the body surface area assessment (BSA). For the estimation of BSA, the palm of the patient (not including the surface of the fingers) is considered to be 0.5% of the total BSA ([Agarwal and Sahu 2010](#)).

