9.5 Analysis of secondary variables

Commercially Confidential
Information

Secondary efficacy variables supporting the secondary objectives are:

- PDAI total score recorded at baseline and weeks 3, 6, 9, 12, 16, 20 and 24.
- ABSIS recorded at baseline and weeks 3, 6, 9, 12, 16, 20 and 24.
- Proportion of patients experiencing control of disease activity at weeks 1, 3, 6, 9, 12, 20 and 24.
- IGA recorded at baseline and weeks 3, 6, 9, 12, 16, 20 and 24.

Commercially Confidential Information

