9.5.1 Efficacy / Pharmacodynamics

The secondary efficacy variables will be analyzed as follows:

The PDAI total score, ABSIS score will be analyzed following the same approach used for the primary efficacy variable.

Commercially Confidential Information

The number and percentage of patients in each category of response for the IGA will be presented for each week.

Commercially Confidential Information

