### 7.2.2 Efficacy / Pharmacodynamics

The secondary Commercially Confidential Information efficacy variables will be analysed as follows:

The PDAI total score, ABSIS score will be analyzed following the same approach used for the primary efficacy variable.

Commercially Confidential Information

## 8

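### In the visible text, Week 12 IGA is only tabulated by category and visit, with no change from each patient's Day 1 score and no VAY736-placebo estimate

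*Protocol*

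**What the plan says.** The objective is stated in the Protocol synopsis and Section 2.2, and again in SAP 2.1.2: "To evaluate the effect of VAY736 in PV patients as assessed by Investigator Global Assessment (IGA) at 12 weeks". The measure is ordinal (Protocol 6.4.3): "An IGA score on a 0-4 scale will be used to assess each patient's PV disease activity". Protocol 9.5 and SAP 7.2 both list the variable with its Day 1 value: "IGA recorded at baseline and weeks 3, 6, 9, 12, 16, 20 and 24".

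The analysis sentence in the Protocol synopsis (Data analysis) is "The number and percentage of patients in each category of response for the IGA will be presented for each visit". Protocol 9.5.1 says the same by week: "The number and percentage of patients in each category of response for the IGA will be presented for each week". I read the categories as the five IGA levels, because no separate response categories are defined.

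The other efficacy variables get more:
- In the synopsis, change in PDAI activity is modelled with the baseline score as covariate, and PDAI total and ABSIS follow a similar approach.
- For disease control, the synopsis plans "The posterior distributions of the difference in proportions between each dose of VAY736 and placebo", with a Beta(1/3, 1/3) prior in each group.
- SAP 7.2.2 refers two scores back to the primary method and, in its visible part, does not mention IGA: "The PDAI total score, ABSIS score will be analyzed following the same approach used for the primary efficacy variable".

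**The concern.** Patients do not all start at the same IGA. Protocol 4.1 admits patients with PDAI 20 to 60 without any IGA limit, "or for a PDAI below 20: an IGA of 2 to 3". A Week 12 IGA of 2 is therefore no change for a patient who began at 2 and an improvement for one who began at 3. A table of category percentages puts both in the same cell.

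The Protocol does use within-patient IGA change elsewhere: Section 5.5.8 ties an increase in standard of care to a worsening of 1 point or more. The visible efficacy analysis does not use it.

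What is at stake is whether the trial can answer its own IGA objective. On the visible text, a reader would compare small cells by eye across arms of 9, 9 and 6, with no estimate, no interval and no view of which patients moved.

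**Working it through.** **No plan figure to reproduce.** Protocol 9.6 covers the primary variable only, and 9.7 gives power for key secondary variables as not applicable. The documents give no IGA distribution, so every IGA input below is an assumption, shown over a range.

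**Step 1. Chance baseline imbalance.** Inputs: 9 patients per dose and 6 on placebo (Protocol 3.1). Let p be the share of patients starting at the worse of two IGA levels, with p = 0.3, 0.5 or 0.7 (assumed). With X ~ Bin(9, p) and Y ~ Bin(6, p), sum the exact probabilities over all pairs where |X/9 − Y/6| reaches the threshold.

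| Gap between arms | p = 0.3 or 0.7 | p = 0.5 |
|---|---|---|
| 25 points or more | 0.307 | 0.344 |
| 33.3 points or more | 0.204 | 0.254 |

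As a check on scale, the SE of the difference at p = 0.5 is √(0.25 × (1/9 + 1/6)) = 0.264. The same sum for the pooled doses (18 v 6) gives 0.251 and 0.296 for 25 points or more.

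**Step 2. How much carries into Week 12.** I simulated a 0-4 score with no drug effect, 9 v 6, from a normal variable cut at −1.5, −0.5, 0.5 and 1.5. Baseline/follow-up correlations of 0.3, 0.5 and 0.7 were assumed.
- Baseline means differ by 0.5 points or more, in either direction, in about 36% of trials.
- When the active arm starts at least 0.5 higher, its unadjusted follow-up mean is higher by 0.21, 0.35 and 0.49 points on average.
- Over all trials the unadjusted difference averages about 0.00, and a 5% test rejects in about 5%.
- Baseline adjustment changes the SD of the estimate from about 0.53 to 0.53, 0.50 and 0.42.

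The gap is thus conditional error in a particular trial, not average bias. The gain from adjustment ranges from nil to about one fifth: 1 − 0.42/0.53 = 0.21.

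**Step 3. Does an own-baseline endpoint detect more?** The figures are the chance that the posterior probability of VAY736 being better exceeds 0.90, for 9 v 6 with Beta(1/3, 1/3) priors. The three values are for 30, 50 and 70% starting at IGA 3, the rest at 2.

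| Assumed response pattern | Improved by ≥ 1 category | IGA 0-1 at Week 12 | IGA 0-2 at Week 12 |
|---|---|---|---|
| A: 70% v 25% improve by one category | 74% throughout | 55, 47, 38% | 39, 42, 52% |
| B: 60% v 15% reach IGA 0-1 from any start; 40% of the remaining IGA 3 patients move to 2 in both arms | 66, 60, 54% | 76% throughout | not computed |

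The ranking reverses between A and B, so neither endpoint is better in general. With 25% improving in both arms, the improvement endpoint still passes 0.90 in about 14% of trials.

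**Step 4. What the added output would look like.** Suppose 6/9 v 1/6 improve. The posterior means are (6 + 1/3)/(9 + 2/3) = 0.655 and (1 + 1/3)/(6 + 2/3) = 0.200. The difference is 0.455, with a 95% credible interval of about 0.01 to 0.80.

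**The case against.** **Redaction.** Confidential text has been removed after the IGA sentence in the synopsis, on both sides of it in Protocol 9.5.1, and after the PDAI/ABSIS sentence in SAP 7.2.2, which is where an IGA method would sit. A reader might infer that no IGA effect estimate is planned at all. The documents do not support that, because such a method may be in the removed text. This stands, and it limits the point to what can be read.

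**Baseline is not plainly ignored.** IGA is recorded on Day 1, and a by-visit table can include that column, so an arm-level imbalance could be seen. This also stands. Such a table cannot show which patients moved.

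**Imbalance is ordinary noise.** A reader might infer that the tabulation is biased. Step 2 shows that it is not, on average. One qualification applies. Under the staggered allocation in Protocol 5.2 (2:0:1, then 1:3:1), 3 of the 6 planned placebo patients but no 10 mg/kg patients enter before the safety review. For that contrast, unbiasedness also assumes no drift in patient mix between the two recruitment stages.

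**Descriptive tabulation is defensible.** The trial is declared non-confirmatory, IGA is one of several secondary measures, and the objective does not call for a formal test. This lowers the weight of the point. It does not remove the contrast with disease control, also a secondary variable, for which an estimate is planned.

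**Conclusion.** The point holds for the visible text. A named Week 12 objective has only category counts and percentages, without a within-patient change from Day 1 and without a comparison against placebo. Chance baseline gaps of 25 points or more between 9 and 6 patients are common, at about 31-34%. This assumes two baseline IGA levels with 30-70% of patients at the worse one. In one trial such a gap can be mistaken for an effect.

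A further inference to avoid is that an own-baseline endpoint would raise the chance of detecting an effect. Step 3 shows that this depends entirely on the assumed response pattern. In a small non-confirmatory trial this is a cheap improvement, not a flaw that threatens the conclusions.

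**What to change.** In the Protocol synopsis, Protocol 9.5.1 and SAP 7.2.2, add:

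1. A shift table of Day 1 IGA by Week 12 IGA for each arm.
2. One pre-specified descriptive Week 12 contrast that uses each patient's own Day 1 IGA, for example the proportion improved by at least 1 category. Report the posterior difference from placebo with a credible interval, for each dose and for the doses combined, under the Beta(1/3, 1/3) prior already planned for disease control.

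If the redacted text already does this, a cross-reference is enough.

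**Cost.** Two outputs from data already scheduled on Day 1 and at Week 12, using a method already planned. No visit, procedure or clinical rule changes.

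**Downside.** Improved/not improved discards the size of the change, which the shift table keeps. It may do worse than IGA 0-1, depending on how patients respond. Because a 90% posterior reading would give a false signal in about 14% of trials when 25% improve in both arms, the contrast should carry no decision rule.
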